Official Title: Revolutionizing Normative Re-education: Delivering Enhanced PNF Within a Social Media Inspired Game About College Life

NCT04356261

Protocol with Statistical Analysis Plan

Document Date: 10/7/25

Background

The transition into college is considered a critical period in which risky drinking patterns are often established (Arria et al., 2016; Derefinko et al., 2016), and serious negative consequences occur (Caamaño-Isorna et al., 2017; Hingson et al., 2009, 2016; Mallett et al., 2013). As perceptions of peers' drinking are among the strongest predictors of college students' future drinking (Borsari & Carey, 2003; Neighbors et al., 2007), but students tend to overestimate these norms (Larimer et al., 2004; Miller & Prentice, 2016), interventions designed to correct misperceived drinking norms have become popular strategies for reducing alcohol-related risks. One such strategy is Personalized Normative Feedback (PNF), wherein students are prompted to answer questions about their perceptions of peers' drinking, report their own drinking, and then receive an individualized report employing a combination of charts and text to highlight discrepancies between perceptions of peers' drinking, peers' actual drinking, and one's own drinking (Larimer & Cronce, 2007). Although studies have reliably found PNF interventions to be efficacious in reducing perceptions of drinking norms, typical weekly alcohol consumption, peak drinks consumed on one occasion (Berkowitz et al., 2005; Lewis & Neighbors, 2007; Miller & Prentice, 2016; NIAAA, 2019), and increasing the likelihood of continued abstinence among non-drinking students (e.g., Bernstein et al., 2018; Larimer et al., 2007; Larimer et al., 2023), the effect sizes associated with these intervention trials have been modest regardless of alcohol risk characteristics of the sample or length of follow-up period for web-based PNF, the most cost-effective and scalable modality (Dotson et al., 2014; Palfai et al., 2014; Rodriguez et al., 2015). Several issues may explain the relatively small effects observed. For example, students often question the credibility of the normative data (Hummer et al., 2016; LaBrie et al., 2010), the content fails to capture students' attention (Lewis & Neighbors, 2007), and heavy drinkers often react to the feedback defensively (Leffingwell et al., 2007; Miller & Leffingwell, 2013). These issues are not surprising as, unlike social media and digital gaming applications that capture and sustain young adults' attention, traditional PNF formats lack the sophisticated digital graphics, social interactivity, and other dynamic features to which students have become accustomed. Inspired by the digital formats and platforms popular among young people, the present study evaluates a modern gamified approach to delivering PNF on alcohol use and other topics of interest to students within a fun, social guessing game for Apple and Android smartphones called CampusGandr.

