This study utilized a three-arm parallel-group randomized controlled trial to examine the efficacy of CampusGandr as a gamification approach to multi-dose PNF for reducing first-year college students' alcohol use. Outcomes were conceptualized in three domains: (1) descriptive norms, (2) alcohol consumption (drinks during a typical week and during one's heaviest drinking occasion), and (3) alcohol-related consequences. All assessments and interventions were implemented remotely, and participants did not interact directly with any research staff. To examine long-term effects, outcomes were measured at 4, 9, and 12 months after baseline.

Participant Recruitment

The present study's primary recruitment sites were a large, public university in Texas (TX) and a small, private college in California (CA). At the beginning of the 2022 and 2023 fall semesters, incoming students from these two universities were invited to create a CampusGandr account via emails and in-person information booths on campus. From Weeks 5 to Week 8, app users were invited to join the study as "Official Testers" and receive \$25 in gift cards for completing the baseline survey. Concurrently, students who didn't yet have accounts were invited via school email to become Official Testers by completing the baseline survey, downloading and creating a CampusGandr account, and begin playing the rounds. All recruitment materials and procedures were reviewed and approved by the universities' IRBs.

To improve participant enrollment for Fall 2023, recruitment efforts were supplemented through BuildClinical (BC), a digital platform specializing in targeted research recruitment. BuildClinical designs and deploys advertisements across a range of online channels, including search engines (e.g., Google) and social media platforms (e.g., Instagram, Snapchat, and Facebook). For this study, BC developed tailored advertisements targeting incoming first-year students at four-year public and private universities in Texas and California (to align with the study's in-person recruitment sites). Individuals who clicked on the ads were directed to a landing page and then a screening survey hosted by BC to assess eligibility. Eligible leads were then directed to our survey hosted on Qualtrics, where we obtained informed consent and administered the survey and invited them to download and play the game.

Procedure

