In total 2,898 students consented and then took the baseline survey and/or played CampusGandr. Of those, 1,143 students were considered fully enrolled in the study, as they provided consent, completed the baseline survey, and played at least one round of CampusGandr. Participants were randomized using an automated urn strategy so that each of the three conditions were filled evenly by a gender and baseline drinking status (any, none). All PNFs were delivered remotely and automatically; therefore, participants, but not researchers, were blind to allocation. Based on condition assignment, participants could see up to 6 alcohol feedbacks (More Alcohol Feedback; MAF), up to 3 alcohol feedbacks (Less Alcohol Feedbacks; LAF) or 0 alcohol feedbacks (No Alcohol Feedback; NAF) during the weekly game. Participants were unaware of study condition, and randomization was not based on any variables. Condition assignment to the LAF and MAF conditions did not guarantee that the participants played the round (i.e., estimating their peers' answer and providing their own answer) and viewed the results (i.e., PNF). Approximately 31% ($n=130$) of participants in the MAF condition saw all 6 alcohol feedbacks and 37% ($n=137$) of participants in the LAF condition saw all 3 alcohol feedbacks. On average, participants in the MAF condition saw 3.0 alcohol feedbacks ($SD=2.6$), and participants in the LAF condition saw 1.5 alcohol feedbacks ($SD=1.3$).

Survey Measures

Descriptive Drinking Norms

Estimates of peers' drinking quantity was measured using the Drinking Norms Rating Form (Baer, 1994). Participants reported the number of standard drinks they believed that a same-gender peer consumed on each day of the week (e.g., a typical Friday, a typical Saturday) in the past 30 days. Participants were asked to think about, "a typical [*male/female/student*] at [*specific college name*]" when answering. Responses were summed across the 7 days, and the sums were truncated at 80.

Injunctive Drinking Norms

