The Injunctive Norms Questionnaire (Baer, 1994) assessed participants' personal approval and perceptions of the approval of a typical same-sex first-year student at their specific university for five risky drinking behaviors including "playing drinking games," "drinking shots," "drinking to get drunk," "drinking alcohol every weekend," and "drinking under age 21." Response options ranged from 1 (*strongly disapprove*) to 7 (*strongly approve*). Internal consistency was high in $\alpha = .89$ for and responses were averaged to create a composite score.

Heaviest Drinking Occasion (Peak Drinks)

Participants were instructed to think about their drinking in the past 30 days and respond to the question, "What is the maximum number of drinks you drank during any one drinking occasion?" Values were truncated at 30.

Typical Weekly Drinking

Typical drinking was measured using the Daily Drinking Questionnaire (Collins et al., 1985). Participants were asked to report the number of standard drinks they consumed on each day (e.g., a typical Monday, Tuesday) of the week during the past 30 days. Responses were summed across the 7 days, and the sums were truncated at 80.

Alcohol-Related Problems

Problems arising from alcohol use were measured using the Brief Young Adult Alcohol Consequences Questionnaire (Kahler et al., 2005). Participants indicated (no=0, yes=1). if they

had experienced 24 negative experiences after drinking alcohol (e.g., “I have felt very sick to my stomach or thrown up after drinking”). Responses were summed, with total scores ranging from 0 to 24. Cronbach’s alphas were acceptable across the four timepoints ($\alpha=0.89-0.92$).

App Measures

Number of Game Feedbacks Viewed

Whether or not participants viewed each round of game feedback was recorded in the app’s backend. This allowed us to create variables indicative of (1) the total number of feedback viewed; and (2) the number of alcohol-specific feedback viewed.

Statistical Analysis Plan

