Modeling Time. To test the intervention’s effects on outcomes at each follow-up, Step 1 of each model evaluated outcomes while controlling for baseline values, sex, site, and follow-up time point. Data from all enrolled participants were utilized in the analyses as modern approaches to handling missing data mostly recover power that would otherwise be lost to attrition (Enders, 2010).

Power. Assuming that the average abstinence rate would be 30% in each condition and baseline outcomes account for 25% of the variance in any drinking at follow-up, the *a priori* power analysis indicated that a sample of 1,200 would yield .89 power to detect abstinence rates as small as 5% lower than control in addition .87 to detect predicted differences among

conditions with rate ratios of 1.2 (i.e., 20% differences or higher between contrast groups). No interim analyses were conducted, nor stopping guidelines were in place.

References

- Arria, A. M., Caldeira, K. M., Allen, H. K., Vincent, K. B., Bugbee, B. A., & O'Grady, K. E. (2016). Drinking like an adult? Trajectories of alcohol use patterns before and after college graduation. *Alcoholism: Clinical and Experimental Research*, 40(3), 583-590.
- Baer, J. S., Stacy, A., & Larimer, M. (1991). Biases in the perception of drinking norms among college students. *Journal of Studies on Alcohol*, 52(6), 580–586.
<https://doi.org/10.15288/jsa.1991.52.580>
- Berkowitz, A.D. (2004). An overview of the social norms approach. In L. Lederman and L. Stewart (Eds.), *Changing the culture of college drinking* (pp. 193–214). Cresskill, NJ: Hampton Press.
- Bensley, L. S., & Wu, R. (1991). The role of psychological reactance in drinking following alcohol prevention messages 1. *Journal of Applied Social Psychology*, 21(13), 1111-1124.
- Bernstein, M. H., Stein, L. A., Neighbors, C., Suffoletto, B., Carey, K. B., Ferszt, G., ... & Wood, M. D. (2018). A text message intervention to reduce 21st birthday alcohol consumption: Evaluation of a two-group randomized controlled trial. *Psychology of Addictive Behaviors*, 32(2), 149-161.
- Borsari, B., & Carey, K. B. (2003). Descriptive and injunctive norms in college drinking: A meta-analytic integration. *Journal of Studies on Alcohol*, 64(3), 331-341.

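### The drinking and problems models, as naturally read, omit baseline descriptive norms: a small loss of precision in the randomised comparison and a possible confounder in the feedbacks-viewed analysis

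*Combined protocol and SAP*

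**What the plan says.** The paragraph on modelling time in the Statistical Analysis Plan holds the only covariate list: "Step 1 of each model evaluated outcomes while controlling for baseline values, sex, site, and follow-up time point". It does not define baseline values, and it describes no step after Step 1. The power paragraph credits only baseline outcomes with explaining variance (25%, for any drinking at follow-up). This supports reading baseline values as each outcome's own baseline. No section names baseline norms as a covariate in a drinking or problems model.

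The Background states that "perceptions of peers' drinking are among the strongest predictors of college students' future drinking". Under Survey Measures, "Estimates of peers' drinking quantity was measured using the Drinking Norms Rating Form", summed over seven days and truncated at 80. The Design section makes these norms an outcome: "Outcomes were conceptualized in three domains: (1) descriptive norms, (2) alcohol consumption". It adds that "outcomes were measured at 4, 9, and 12 months after baseline".

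**The concern.** The plan names a strong predictor of the outcome, appears to hold it for every enrolled student, and then seems to leave it out of the models for that outcome. Two things are at stake.

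- **Intent-to-treat contrasts.** A prognostic covariate measured before the intervention can sharpen the arm comparison. Leaving it out forgoes whatever precision it adds beyond the covariates already listed.
- **Feedbacks-viewed analysis.** Here the exposure is the number of alcohol feedbacks a student actually opened. If baseline norms relate both to continued play and to later drinking, leaving them out could distort the estimated dose effect.

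**Working it through.** **1. Is a baseline norm score available, and does it precede the intervention?** The documents do not state separately that norms were in the baseline survey. It follows from two statements: descriptive norms are an outcome domain, and each model controls for baseline values. Under Procedure, completing the baseline survey is an enrolment condition, recruitment closed in week 8, and the first alcohol feedback came in week 9. The score therefore precedes all alcohol feedback, and adjusting for it cannot remove an effect that works by changing norms. The urn balanced gender and any/none baseline drinking, not norms.

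**2. The plan's own power figure.** The stated power is .89 with 1,200 students, abstinence of 30% against 25%, and 25% of variance explained. The check assumed two-sided alpha .05, which the plan does not state, and treated the 25% as an effective-n gain:

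- 400 per arm: effective n = 400/.75 = 533 per arm, power .448.
- 1,200 per arm: effective n = 1,200/.75 = 1,600 per arm, power .887.

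The .89 is thus not reproduced with 1,200 as a three-arm total at one time point. That is a separate matter and does not arise from the missing covariate. The .87 for a rate ratio of 1.2 cannot be checked, because no mean or dispersion is given.

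**3. Linear approximation of the precision forgone.** Let r1 be the correlation of own baseline with follow-up drinking, r2 that of baseline norms with follow-up drinking, and r12 that of norms with own baseline. Then

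R² = (r1² + r2² − 2·r1·r2·r12) / (1 − r12²)

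The plan's 25% gives r1 = .50. The values of r2 (.30 to .45) and r12 (.30 to .50) are assumptions. Equivalent students = 1,143 × [(1 − r1²)/(1 − R²) − 1].

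| r2 | r12 | R² | Cut in residual variance | Equivalent students |
|---|---|---|---|---|
| .30 | .50 | .19/.75 = .253 | 0.4% | 5 |
| .40 | .40 | .25/.84 = .298 | 6.3% | 77 |
| .45 | .30 | .3175/.91 = .349 | 13.2% | 174 |

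The result depends heavily on r1. With r2 = .40 and r12 = .50, the cut is 4.0% at r1 = .50, 2.1% at .60 and 0.7% at .70. With r1 = .60, r2 = .30 and r12 = .50 it is zero, since R² = .27/.75 = .36 = r1².

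**4. In terms of power.** If norms explain a further share q of the residual variance, power = Φ((z + 1.96)/√(1 − q) − 1.96), where z is the normal quantile of the starting power.

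| q | From .89 | From .87 | From .448 |
|---|---|---|---|
| .01 | .893 | .873 | .451 |
| .05 | .905 | .886 | .467 |
| .10 | .919 | .902 | .487 |
| .15 | .933 | .917 | .509 |

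**5. Logistic simulation.** Assumptions: 400 per arm, own baseline explaining 25% of latent variance, norms correlated .5 with baseline drinking, 1,500 runs per setting. Adding norms moved power from .526 to .529, from .467 to .475 and from .479 to .503, gains of 0.3 to 2.4 points. The Monte Carlo standard error of one such power figure is about √(.5 × .5/1,500) = 1.3 points, so the smaller gains are hard to tell from none. Type I error was .043 to .054 with or without norms, close to .05.

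**6. The feedbacks-viewed analysis.** Under Procedure, students allocated up to 6 alcohol feedbacks saw 3.0 on average (SD 2.6), and those allocated up to 3 saw 1.5 (SD 1.3). About 31% and 37% saw all of theirs. Much of the variation in dose is therefore within arm and depends on whether the student played and opened the results. Randomisation does not protect that comparison. The documents give no association between baseline norms and viewing, so neither the size nor the direction of any confounding can be calculated.

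**The case against.** The strongest case on the other side is that this is a preference and not an error. The intent-to-treat comparison is randomised and already adjusted for baseline values, sex and site, and no stated figure is wrong because norms are absent. That stands.

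Four further points also stand:

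- The Background's claim is marginal. It does not say that norms add much once own baseline drinking is in the model, and only that increment matters here.
- The 25% applies to any drinking. Using r1 = .50 for peak drinks, weekly drinks or problems has no support in the documents.
- The models are logistic and truncated negative binomial. A logistic model has no residual variance to remove in the linear sense, and an added covariate changes the conditional odds ratio itself. The count parts use non-zero values only; at the assumed 30% abstinence that is about .70 × 1,143 = 800 students for the drinking counts, so an equivalent out of 1,143 does not carry over.
- Baseline values is undefined and only Step 1 is described. Omission of norms is the natural reading, not an explicit exclusion.

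A reader might infer that chance imbalance in norms leaves the arm contrasts uncorrected and hence biased. The documents do not support that. The part of norms correlated with own baseline drinking is already adjusted for, and the standard error covers the remaining chance imbalance.

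The objection does not answer the feedbacks-viewed analysis, where the issue is confounding and not only precision.

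**Conclusion.** The point holds as a minor improvement. On the natural reading, a covariate that the plan itself calls prognostic, and that precedes the intervention, is absent from the drinking and problems models.

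For the intent-to-treat contrasts the cost is precision alone. It is probably small: 0.3 to 2.4 power points in the simulation, and 0.3 to about 4 points from the stated .89 if norms explain a further 1% to 15% of residual variance. Every one of these sizes rests on assumed correlations. The range of 5 to 174 students is a linear illustration and should not be read as a sample-size shortfall.

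For the feedbacks-viewed analysis the omission could also confound the dose estimate, to an extent the documents do not allow anyone to quantify. It would go too far to say that this estimate is shown to be biased.

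**What to change.** Add the baseline descriptive-norm score (the seven-day sum truncated at 80) as a covariate in both parts of the peak-drinks and problems models and in the weekly-drinks model. Do this for both the intent-to-treat and the feedbacks-viewed strategies. In the same paragraph, define baseline values and list every modelling step.

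Report the results as a labelled adjusted sensitivity analysis beside the stated models, not in place of them. The document is dated 10/7/25, covers the 2022 and 2023 cohorts and describes its analyses in the past tense, so replacing the main models now would be a post hoc change.

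The cost is one degree of freedom per model part and a small change to code and text, using data already held. The odds ratios will be conditional on one more covariate, so they are not directly comparable with those from the stated models. In the feedbacks-viewed models the adjustment can reduce confounding by norms; it cannot deal with other reasons why some students kept playing.

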Building on this work and in response to calls in the literature to explicitly examine changes in perceived drinking norms and alcohol outcomes in PNF intervention studies (e.g., Dempsey et al., 2018), this study employed a large and diverse sample of incoming college students attending universities in Texas and California to (1) examine the effectiveness of a fully featured CampusGandr smartphone app as an alcohol intervention strategy when advertised to students as a social game about college life free to play over their fall semester; and, (2) elucidate the optimal dosage of alcohol feedback to be delivered in the app to best reduce perceptions of drinking norms and alcohol consumption. First, using an intent-to-treat approach, we examine short and longer-term effects on alcohol use and perceptions of drinking norms associated with a CampusGandr intervention period in which student users were randomized to receive alcohol feedback in 0, 3, or 6 weeks of the game. Second, we take a closer look at the question of dosage by examining end-of-semester drinking and perceptions of norms as a function of the number of alcohol feedback results verifiably viewed by participants. Whereas a traditional alcohol intervention approach might assume that delivering alcohol feedback every week would be most protective, our pilot work (Boyle et al., 2018) and a large psychological reactance literature (e.g., Dillard et al., 2023; Jung et al., 2010; Reynolds-Tylus et al., 2022, 2024) suggest that too much feedback on alcohol relative to other topics in the game may reveal the drinking-reduction intention of the activity, eliciting reactance, and thereby undermining efficacy. As such, less frequent alcohol feedback balanced with feedback on other topics of interest to students was expected to be more efficacious in reducing perceived drinking norms, preventing alcohol

initiation, and reducing consumption than both no alcohol feedback and more frequent alcohol feedback.

Design

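### The stated .89 power for a 5-point abstinence difference cannot be reproduced from the plan's inputs; a pairwise contrast at one follow-up with 400 per arm has about .45, and the stated direction runs against the hypothesis

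*Combined protocol and SAP*

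**What the plan says.** All places are in the combined protocol and SAP.

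- **Statistical Analysis Plan, Power:** the calculation begins "Assuming that the average abstinence rate would be 30% in each condition" and takes it that "baseline outcomes account for 25% of the variance in any drinking at follow-up". From these it concludes that "a sample of 1,200 would yield .89 power to detect abstinence rates as small as 5% lower than control". It gives no alpha, sidedness, contrast, time structure or within-person correlation.
- **Design:** the trial is a "three-arm parallel-group randomized controlled trial" with surveys at 4, 9 and 12 months.
- **Procedure:** the three conditions were to be filled evenly, and "1,143 students were considered fully enrolled in the study".
- **Goals of This Clinical Trial:** less frequent alcohol feedback was "expected to be more efficacious in reducing perceived drinking norms, preventing alcohol" initiation, and reducing consumption, compared with no alcohol feedback and with more frequent feedback.
- **Statistical Analysis Plan, Modeling Time:** effects are to be tested at each follow-up in models that adjust for baseline, sex, site and time point. All enrolled participants are analysed, on the ground that missing-data methods recover most of the power that attrition would cost.

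**The concern.** For 30% against 25%, a power near .9 needs well over a thousand students per group. Here 1,200 can only be the whole trial: enrolment is reported as 1,143 over all three arms. A power of .89 is therefore implausible on its face for two groups of about 400.

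The direction is also odd. The paragraph powers the trial for "abstinence rates as small as 5% lower than control", that is, for more students drinking under feedback. The stated expectation is the reverse.

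Any drinking is the logistic part of the hurdle model for peak drinks, and it is where the prevention hypothesis is tested. A reader who trusts .89 would take a null result there as good evidence against a 5-point effect. On the plain pairwise reading, the trial would miss such an effect more often than not.

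**Working it through.** **Inputs from the document:** control abstinence .30; difference .05, read as percentage points; baseline R² = .25, so residual variance is multiplied by .75; 1,200 in three equal arms, 400 per arm.

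**Assumed, because not stated:** two-sided 5% test (one-sided also tried); no loss to follow-up, which favours the stated figure.

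**Formula:** SE = √{.75 × [p₁(1−p₁)/n₁ + p₂(1−p₂)/n₂]}; z = .05/SE; power = Φ(z − 1.960), or Φ(z − 1.645) one-sided.

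**1. Attempt to reproduce .89, pairwise at one follow-up**
- 400 v 400: SE = √[.75 × (.21 + .1875)/400] = .0273; z = 1.83; power **.449** (.354 without the R² adjustment).
- 1,200 v 1,200: SE = .0158; z = 3.17; power **.887**.
- Sample size for .89: (1.960 + 1.227)² × .3975 × .75/.05² ≈ 1,211 per arm.
- Hypothesised direction, 30% v 35%: at 400 per arm, SE = √[.75 × (.21 + .2275)/400] = .0286; z = 1.75; power **.415**. At 1,200 per arm it is .856.

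**2. Other readings with 1,200 in total and one follow-up (30% v 25% unless shown)**

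| Reading | Power |
|---|---|
| 400 v 400, one-sided | .57 |
| 32.5% v 27.5%, two-sided | .43 |
| Relative 5% (30% v 28.5%), two-sided | .08 |
| Both feedback arms pooled (800) v control (400), two-sided | .55 |
| The same, one-sided | .67 |
| All 1,200 in two arms (600 v 600), two-sided | .61 |
| Omnibus 2-df test, one or both feedback arms 5 points lower | .45 to .46 |

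None reaches .89. The omnibus test gives about .90 only if the arms lie at 35/30/25, a spread of 10 points.

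**3. Averaging the three surveys**

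With residual within-person correlation ρ, the variance is multiplied by (1 + 2ρ)/3. The values of ρ are assumed. All figures are for 30% v 25%, two-sided.

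| ρ | Pairwise, 400 v 400 | Pooled, 800 v 400 |
|---|---|---|
| 0 | .89 | .95 |
| .2 | .76 | .87 |
| .4 | .66 | .77 |
| .7 | .53 | .65 |

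At ρ = 0 the pairwise figure is the same .887, because 3 × 400 = 1,200 observations per arm. A power of .89 needs ρ of about 0 (pairwise, two-sided), .11 (pairwise, one-sided), .15 (pooled, two-sided) or .3 (pooled, one-sided).

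**4. What 400 per arm detects with .89 power (pairwise, one follow-up, two-sided)**
- Lower: 30% v 21.5% gives z = 3.19 and power .89, a difference of about 8.5 points.
- Higher: 30% v 39.3% gives z = 3.21 and power .89, a difference of about 9.3 points.

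**5. At the enrolled number:** 1,143/3 = 381 per arm gives .43 (25%) and .40 (35%), before any loss.

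**The case against.** The strongest reply is that .45 belongs to one reading only. The plan does not state alpha, sidedness or contrast. The analysis is a mixed model over three surveys with time point as a covariate, so an effect averaged over time is a possible target, and pooled feedback against control is not excluded. The correlation that matters is also the one left after baseline adjustment. If baseline correlates .5 with each follow-up (R² = .25), a raw correlation of .4 between follow-ups becomes (.4 − .25)/.75 = .20. Power is then about .76 pairwise and .87 pooled.

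This stands in part. It shows that .45 is the low end of a range that depends on design choices the plan leaves open, so .45 should not be presented as the power of every planned analysis. It does not restore .89. That figure still needs a very low residual correlation, or pooling together with a low one, and the document states neither. The plan's text points the other way: effects are tested at each follow-up, and the hypothesis sets less feedback against none and against more, which are pairwise contrasts.

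Two further replies are fair. First, the plan does address attrition through its missing-data statement, so it cannot be said to ignore it, although no loss is built into the power figure. Second, enrolling 1,143 does not make an advance statement about 1,200 wrong; it moves the pairwise figure only from .45 to .43.

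A reader might infer that the authors mistook a per-arm number for a total. The match at .887 invites this, but three surveys counted as independent match equally well, and in the hypothesised direction 1,200 per arm gives .856. The source cannot be determined from the documents.

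**Conclusion.** The point holds as a failure to reproduce. With 30% abstinence, R² of .25 and 1,200 students in three equal arms, the stated .89 does not follow for a 5-point difference. Under an assumed two-sided 5% test, a pairwise contrast at one follow-up has about .45 (25%) or .42 (35%). Averaging the surveys gives about .76 to .53 pairwise, or .87 to .65 pooled, for assumed residual correlations of .2 to .7. All these figures assume no loss to follow-up.

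The direction is wrong relative to the stated hypothesis. This is a separate and smaller matter, worth about three points of power in the pairwise case. It should not be read as a sign that the investigators expected harm.

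Nor should a reader infer that the companion .87 for a rate ratio of 1.2 is wrong. No mean or dispersion is given, so it cannot be checked. The correction changes no data, model or estimate. It changes how much a null abstinence result can be said to show.

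**What to change.** Restate the abstinence power with its alpha, sidedness, contrast and time structure. For example:

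> With 400 per arm and a two-sided 5% test, power for a 5-point pairwise difference in abstinence at one follow-up is about .45 (.42 for an increase). Power of .89 applies to a difference of about 8.5 points lower or 9.3 points higher.

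If a repeated-measures or pooled contrast was intended, give that power instead, with the assumed residual within-person correlation. Change the direction to higher abstinence than control, to agree with the Goals section. Say that the figure includes no loss to follow-up and that the plan relies on its missing-data approach for this.

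In reporting, give the confidence interval for the abstinence contrast and do not present a null result as evidence against a 5-point effect.

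The cost is one paragraph and no new data. On the plain pairwise reading, the stated power becomes less favourable.
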